4.8.6 Patient Reported Outcomes (PROs)

4.8.6.1 Work Limitations Questionnaire 8-Item (WLQ-8) Self-administered Short Form

The WLQ-8 questionnaire (Protocol Appendix 2-2) is an 8-item instrument used to assess the degree to which subjects have difficulty related to time management, physical tasks, mental/interpersonal tasks, and output tasks due to their physical and/or emotional health. The WLQ-8 produces 4 subscale scores as well as an index of overall at-work productivity loss. Subjects will self-administer these instruments on paper at visit 1, visit 7, and visit 13.

WLQ-8 Scoring Information

General Information:

Scale response options are as follows: “all of the time (100%)”; “most of the time”; “some of the time (approximately 50%)”; “a slight bit of the time”; “none of the time (0%)”; and “does not apply to my job”. The time management, mental-interpersonal, and output subscale items address the amount of time that physical or emotional health problems made the performance of specific demands difficult. The physical scale refers to the amount of time the employee was able to perform a demand without difficulty due to health problems. The recall period is the past 2 weeks.

Questions:

Q1 = get going easily at the beginning of the workday

Q2 = start on your job as soon as you arrived at work

Q3 = sit, stand, or stay in one position for longer than 15 minutes while working

Q4 = repeat the same motions over and over again while working

Q5 = concentrate on your work

Q6 = speak with people in-person, in meetings or on the phone

Q7 = handle the workload

Q8 = finish work on time

Scores:

In general, WLQ-8 outcomes are expressed as index scores, with higher numbers indicating greater limitations, i.e., worse outcomes. The WLQ-8 questionnaire includes two questions for each subscale. Each of the four subscale scores are computed as the mean of the non-missing responses from both questions. With the exception of data evaluating physical tasks (Q3 & Q4), data will be recoded so that 1 represents “none of the time (0%)” and 5 represents “all of the time (100%)”. Values of “does not apply to my job” will be set to missing for the calculation of subscale scores. The at-work productivity loss score is computed as the mean of the non-missing responses from all 8 questions.

1. Time management: Q1 & Q2
2. Physical tasks: Q3 & Q4
3. Mental/Interpersonal tasks: Q5 & Q6
4. Output tasks: Q7 & Q8
5. At-Work Productivity Loss: Q1 - Q8

The four subscales and the overall at-work productivity loss will be calculated at baseline, month 6 (visit 7), and month 12 (visit 13). Change from baseline will be calculated for each score at month 6 (visit 7) and month 12 (visit 13).

4.8.6.2 Work Productivity and Activity Impairment: Specific Health Problems Questionnaire v2.0 (WPAI:SHP)

The Work Productivity and Activity Impairment: Specific Health Problems (WPAI:SHP) questionnaire is a 6-item instrument that measures absenteeism (work time missed), presenteeism (impairment while working), work productivity loss (overall work impairment), and activity impairment due to a target health problem, namely excess body weight, in the past seven days. Subjects will self-administer these instruments on paper at visit 1, visit 7, and visit 13. (Protocol Appendix 2-1).

WPAI:SHP Scoring Information

General Information:

In general, WPAI:SHP outcomes are expressed as impairment percentages, with higher numbers indicating greater impairment and less productivity, i.e., worse outcomes. The recall period is the past seven days, excluding the current day.

Questions:

Q1 = currently employed (Yes=works full-/part-time; self-employed; works in family business; on vacation from paid employment/No=does not work for pay; only does volunteer work; usually works, but has been laid-off or unemployed during the past seven days; retired; seasonal workers not currently working)

Q2 = hours missed due to specified problem

Q3 = hours missed for other reasons

Q4 = hours actually worked

Q5 = degree problem affected productivity while working

Q6 = degree problem affected regular activities

Scores:

Multiply scores by 100 to express in percentages

1. Percent work time missed due to health (Absenteeism): $Q2/(Q2 + Q4)$
2. Percent impairment while working due to health (Presenteeism): $Q5 / 10$
3. Percent overall work impairment due to health (Work Productivity Loss): $Q2/(Q2 + Q4) + [(1 - (Q2/(Q2 + Q4))) \times (Q5/10)]$
4. Percent activity impairment due to health (Activity Impairment): $Q6/10$

Absenteeism, presenteeism, work productivity loss, and activity impairment will be calculated at baseline, month 6 (visit 7), and month 12 (visit 13). Change from baseline will be calculated for each score at month 6 (visit 7) and month 12 (visit 13).

4.9 Examination of Subgroups

There are no subgroup analyses planned for this study.

5.0 STATISTICAL ANALYSES

5.1 Overview

Once data collection of the last subject visit and data management activities have been completed, database lock will occur and all analyses outlined in this SAP will be performed. Analyses results will be presented in a clinical study report and at an internal results meeting.

Descriptive summaries will be produced for both the primary (ITT) and secondary (“if all patients adhered”) estimands. All statistical analyses will be conducted under both the primary estimand (ITT) and secondary estimand (“if all patients had adhered”), with the exception of the secondary endpoints for adherence to treatment, which will be based on the primary estimand only.

5.2 Patient Disposition and Accountability

Patient disposition will be descriptively summarized for all randomized patients overall and by treatment group, including the number and percentage patients in the FAS population, patients who completed study (defined as subjects with month 12 (visit 13) body weight data), and the primary reason for not completing the study for patients who terminated participation in the

study early. Summary metrics for number of screen failures will also be presented. A flow diagram (e.g.: Consort flow diagram) of patient disposition will also be created.

5.3 Demographics and Baseline Clinical Characteristics

Demographic and baseline clinical characteristics will be descriptively summarized for the FAS overall and by treatment group. For baseline comorbid conditions (medical history and concomitant illnesses), the number and percentage of patients with at least one of the comorbid conditions collected in the study will also be summarized along with the relative frequencies of type of comorbid condition. For baseline concomitant medications, the relative frequencies of the types of concomitant medications at the time of enrollment categorized by indication will be summarized.

5.4 Protocol Deviations

Major protocol deviations will be summarized by type (e.g.: informed consent, randomization error, inclusion/exclusion criteria error, unreported serious adverse events (SAEs), treatment violation, study visit not per protocol, other).

5.5 Missing Value Imputation Methodology

5.5.1 Body Weight

Missing endpoint data will be imputed for body weight at month 12 (visit 13). These data will be used for the analysis of the primary estimand for the primary endpoint and the analysis of the primary estimand for the secondary endpoint of categorical weight loss.

The primary approach for imputation of missing values of body weight at visit 13 is imputations by sampling among all available assessments at visit 13 in the WMP arm (including values from retrieved subjects). This approach is also known as “jump to reference” and makes the assumption that subjects instantly after discontinuation lose any effect of randomized treatment beyond what can be expected from the WMP. Body weight measurements at visits between baseline and visit 13 are not used for this imputation approach.

The multiple imputation approach is done in three steps.

1. **Imputation:** Step 1 defines an imputation model based on WMP arm subjects, which is used to impute missing body weight values at visit 13 in both arms. This will be done 100 times.
2. **Analysis:** Step 2 analyses each of the 100 complete data sets, using the statistical model described above and saves the 100 estimation results.
3. **Pooling:** Step 3 integrates the 100 estimation results into a final result using Rubin’s formula [5].

The imputation model in step 1 uses WMP arm subjects from FAS with non-missing body weight measurements at baseline and visit 13 (including values from retrieved subjects). The

imputation model is a linear regression of body weight (kg) at visit 13 with gender (male/female), BMI (kg/m²) in categories 30-<35, 35-<40, ≥40 as factors and baseline body weight (kg) as covariate. No interactions will be included. The estimated posterior distribution for the parameters (regression coefficients and variances) in the imputation model is then used to impute missing visit 13 body weight values for both randomized treatment arms.

If 100 copies are not sufficient to establish stable results, a higher number will be used. The multiple imputations will be generated using Novo Nordisk trial number 80224432 as seed number, and will be executed using the PROC MI and PROC MIANALYZE procedures in SAS.

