6 STATISTICAL METHODS

6.1 Analysis Overview

Subjects will be randomized 1:1 to WMP + Rx or WMP alone. The data analyses for this study will be outlined in further detail in a Statistical Analysis Plan (SAP).

The significance level used in all statistical analyses will be 5% (two-sided).

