6.3 Sample Size Determination

6.3.1 Power and Sample Size for Primary Objective

Assumptions for sample size calculations included:

- Two sample two sided t-test with equal variances
- 5% significance level, but superiority is only claimed if estimated difference in mean weight loss favors WMP + Rx (this corresponds to a one-sided test on a 2.5% significance level).
- 1:1 randomization
- 50% of subjects in both arms are expected to drop out (based on input from the Cleveland Clinic)
 - Among subjects who drop out, 50% are expected to return for a month 12 (visit 13) assessment (retrieved drop outs).
 - Retrieved and non-retrieved drop outs in the WMP arm are assumed to have the same effect as subjects who complete the WMP arm.
 - Non-retrieved drop outs in the WMP + Rx arm are assumed to have an effect corresponding to subjects in the WMP arm.
 - Retrieved drop outs in the WMP + Rx arm are assumed to have an effect corresponding to half the weight loss difference (compared to WMP) of subjects who complete the study in the WMP + Rx arm.
- The following expected distribution of prescriptions in the WMP + Rx arm (based on input from the Cleveland Clinic):
 - 0% Orlistat (Xenical®)
 - 10% Lorcaserin/Lorcaserin extended-release (Belviq®/BelviqXR)
 - 30% Phentermine/Topiramate extended-release (Qsymia®)
 - 30% Naltrexone/Bupropion extended-release (Contrave®)
 - 30% Liraglutide 3.0 mg (Saxenda®)

Table 6-1 presents several sample size scenarios and power calculations based on the above assumptions, varying expected mean differences in weight loss between treatment arms (treatment effect) over 1 year and standard deviations (SD) as the variation of weight loss between subjects within the same treatment arm. Treatment effect scenarios of 3, 3.5, 4, and 5% were chosen based on product labels. SD of 8, 9, 10, and 11 % were chosen based on the NN8022 (SCALE) program [18] [19] [20] and the TRAMOMTANA [21] study.

Table 6-1. Power calculations for selected total N, treatment effects, and standard deviations

	Treatment effect (%)															
	3				3.5				4				5			
	SD (%)				SD (%)				SD (%)				SD (%)			
Total N	8	9	10	11	8	9	10	11	8	9	10	11	8	9	10	11
160	0.65	0.55	0.47	0.40	0.79	0.69	0.59	0.52	0.88	0.80	0.71	0.63	0.98	0.94	0.88	0.82
180	0.71	0.60	0.52	0.44	0.83	0.74	0.65	0.56	0.92	0.84	0.76	0.68	0.99	0.96	0.92	0.86
200	0.75	0.65	0.56	0.48	0.87	0.78	0.69	0.61	0.94	0.88	0.80	0.73	0.99	0.97	0.94	0.89

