240	0.82	0.73	0.64	0.56	0.92	0.85	0.77	0.69	0.97	0.93	0.87	0.80	1.00	0.99	0.97	0.94
300	0.90	0.82	0.74	0.65	0.97	0.92	0.86	0.78	0.99	0.97	0.93	0.88	1.00	1.00	0.99	0.98

Total N = sum of subjects in both treatment arms; treatment effect = difference in one-year weight loss of WMP + Rx compared to WMP alone; standard deviation (SD) = variation in weight loss between subjects within the same treatment arm.

Based on the above mentioned assumptions and results from the referenced studies, a 4% treatment effect and 10% SD is a conservative, yet realistic scenario. Therefore, a total sample size of 200 subjects (100 subjects per treatment arm) with 80% power for the confirmatory hypothesis assuming a 25% attrition rate over 12 months was chosen.

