4.0 STATISTICAL METHODOLOGY

4.1 General Considerations

Statistical analyses will be performed using SAS® version 9.4 or higher computer software. Analyses will utilize prospectively collected data from study site at study visits as well as secondary data collection utilizing pharmacy dispensing data. Data from both sources will be integrated into one dataset for analysis.

Patient flow, patient characteristics, treatments, and outcomes will be tabulated and summarized with descriptive statistics based on observed values only. All descriptive data summaries will include means, medians, standard deviation (SD), and ranges for continuous variables and absolute/relative frequencies for categorical data. In addition, for each variable the number (count) of values that are missing will also be reported for dedicated study visit data. Missing data are data that are planned and can be collected but are absent. Statistics will be summarized for the study population overall and by treatment arm. Two sets of descriptive summaries will be produced: one based on the primary estimand (“intention-to-treat” (ITT)) and one based on the secondary estimand (“if all patients had adhered”).

Raw data (i.e., minimum and maximum values presented for range in continuous variables) will be reported out to the precision with which it was collected. Means will be reported to 1 decimal place more than the raw data. SD will be reported to 1 decimal place more than the mean. Percentages will be reported to 1 decimal place. Trailing zeros will be presented to maintain a consistent level of precision, e.g. 2.0 rather than 2.

Inferential tests will be performed at the 5% level of significance (two-sided). All p-values will be rounded to 3 decimal places. If a rounded p-value is 0.000 (i.e., the actual p-value is less than 0.0005), then the p-value will be presented as ‘p< 0.001.’

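### Rubin pooling of the jump-to-reference imputations makes the single confirmatory test conservative: at the planned 25% missingness its size is about 1% and its power about 69–77%, not the stated 80%

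*SAP*

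**What the plan says.** SAP 5.5.1 defines the primary handling of missing month 12 weight. A linear regression of visit 13 weight on sex, BMI class and baseline weight is fitted to WMP subjects with both weights, "which is used to impute missing body weight values at visit 13 in both arms". This is done 100 times, and "Step 3 integrates the 100 estimation results into a final result" by Rubin's formula, run in PROC MI and PROC MIANALYZE. SAP 5.6.1 takes the estimate, 95% CI, p-value and superiority decision from an ANCOVA on these data. SAP 4.1 and protocol 6.1 set a two-sided 5% level.

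Protocol 6.3.1 plans on a "Two sample two sided t-test with equal variances" and adds that, with the directional rule, "this corresponds to a one-sided test on a 2.5% significance level". It judges that "a 4% treatment effect and 10% SD is a conservative, yet realistic scenario" and chooses 200 subjects "with 80% power for the confirmatory hypothesis assuming a 25% attrition rate over 12 months". It expects half of each arm to drop out and half of those to return, so 25% per arm have no month 12 value. Protocol 4.2.5 agrees: 150 of 200 with an on-site final weight.

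Neither document discusses the variance of a reference-based estimate or evaluates power under the specified imputation and pooling.

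**The concern.** Drawing missing WMP + Rx outcomes from the WMP model pulls the two arm means together. That shrinks the estimated difference and also its true sampling variability. Rubin's total variance does not register this. It starts from the variance of a complete data set and adds between-imputation variance on top. The pooled standard error is therefore too large for a test meant to run at 5% two-sided.

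This is the trial's only confirmatory test. A real benefit is more likely to be missed than the protocol tells its readers, and the 95% interval covers more often than 95%.

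**Working it through.** **Inputs.** n = 100 per arm, SD = 10, difference 4, two-sided 5% and 25% missing per arm (protocol 6.3.1); 100 imputations and Rubin pooling (SAP 5.5.1); ANCOVA on treatment and baseline weight (SAP 5.6.1).

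**1. The plan's own figure.** A two-sample t-test with 100 per arm has SE = 10 × √(2/100) = 1.414, and its power for a difference of 4 is 0.804 (noncentral t). All 80 cells of Table 6-1 reproduce within 0.005 this way. The table therefore treats all 200 subjects as observed and the 4 points as the all-randomised difference. With 75 per arm the power would be 0.68.

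**2. Closed form, missing share p in each arm, covariates ignored.**

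- The WMP + Rx mean after imputation is (1−p) × its observed mean + p × the WMP observed mean. The WMP mean is unchanged in expectation. The estimate is (1−p) × the observed difference.
- Repeated-sampling variance: (1−p)² × 2SD²/((1−p)n) = (1−p) × 2SD²/n.
- Rubin's total: within-imputation 2SD²/n plus between-imputation 2pSD²/n = (1+p) × 2SD²/n.
- Ratio of standard errors: √((1+p)/(1−p)).

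At p = 0.25:

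- Rubin SE = √(1.25 × 2) = 1.581. Repeated-sampling SE = √(0.75 × 2) = 1.225. Ratio 1.291.
- Two-sided size = 2 × [1 − Φ(1.96 × 1.291)] = 0.011.
- Power at 4 = Φ((4 − 1.96 × 1.581)/1.225) = Φ(0.736) = 0.769.

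**3. Simulation of the SAP models.** It uses the regression in kg with posterior draws, M = 100, ANCOVA on percent change and Rubin pooling. Sex mix, BMI and height are assumed, since the documents give none.

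- Null, 25% missing, 20,000 runs: empirical SD 1.231, mean Rubin SE 1.655 (ratio 1.35), rejection 0.9% two-sided and 0.4% in the favourable direction.
- The same with residual variance constant in kg, 12,000 runs: 1.233 and 1.617 (ratio 1.31), rejection 1.0% and 0.5%.
- All-randomised difference 4. Under the protocol's drop-out effects this needs a completer effect of 6.4, because 0.5 × 6.4 + 0.25 × 3.2 + 0.25 × 0 = 4.0. Power is 72.5% and 73.9% under the two variance models. Smaller runs with other settings gave 69–70%.

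The closed form does not charge for estimating the imputation model, so simulated power is a little lower.

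**4. Range over missingness, equal in both arms.**

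| Missing | SE ratio, closed form | Two-sided size, closed form (simulated) | Power at 4, closed form (simulated) |
|---|---|---|---|
| 10% | 1.11 | 3.0% (3.2%) | 79% (78%) |
| 15% | 1.16 | 2.3% (2.2%) | 78% (76%) |
| 25% | 1.29 | 1.1% (0.9–1.0%) | 77% (69–74%) |
| 35% | 1.44 | 0.5% (0.4%) | 75% (not run) |

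**5. Unequal missingness** (share t in WMP + Rx, c in WMP). The repeated-sampling variance is (SD²/n)(1−t)²[1/(1−t) + 1/(1−c)]. Rubin's is (SD²/n)[2 + t + c + (t−c)²/(1−c)]. With t = 20% and c = 30%, the ratio is 1.21 and size 1.8%. With t = 30% and c = 20%, they are 1.38 and 0.7%.

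**The case against.** **Rubin's variance is a defensible choice.** The repeated-sampling SE at 25% missing (1.22) is smaller than the SE with no missing data at all (1.41), and it keeps shrinking as data are lost. A test built on it would have about 90% power, more than the 80% of a fully observed trial. Since estimate and SE are both (1−p) times their observed-case values, that test is, covariates aside, the observed-case test. A sponsor may reasonably decline a variance that rewards missing data. This stands, and it is why the fix does not replace Rubin's formula. It does not rescue the 80%, and neither document records the choice.

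**A test whose size is below 5% still respects a 5% level.** This also stands: there is no false-positive inflation. What fails is the power figure, and the one-sided 2.5% as a description of how the test behaves.

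**Missingness may be lower than 25%.** Protocol 5.5 adds call-in, medical-record and self-reported weights. It gives no recovery rate, and 25% is the attrition that the power statement itself assumes. At 10% missing the shortfall is only one to three points.

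**A stronger reading the documents do not support.** A reader might infer that pooling roughly halves the chance of success. That holds only if 4 points is the effect in completers. The protocol's drop-out effects then dilute it to 4 × (0.5 + 0.25 × 0.5) = 2.5 points, and power is about 27–31% with Rubin's SE against 50–53% with a repeated-sampling SE. Table 6-1 does not use that reading. The plain t-test already has only 42% power at 2.5 points, so most of the fall from 80% is dilution, not pooling. On the table's own reading the shortfall from 80% at 25% missing is about 3–11 points.

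**Conclusion.** Wrong as written, of moderate severity. At the plan's 25% missing per arm, the specified analysis has a standard error about 29–35% above the repeated-sampling SD. Its two-sided size is about 1%, or about 0.5% in the superiority direction against the stated 2.5%. Power is about 69–77% for a 4-point all-randomised difference with SD 10. The 80% in protocol 6.3.1 describes a different analysis, a t-test on 200 complete subjects. At 10% missing, size is about 3% and power about 77–79%.

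The direction and most of the size follow from algebra. The simulated figures also rest on assumed sex, BMI and height distributions. The error is conservative, so a positive result is not put in doubt. Nor do the documents support saying that a repeated-sampling SE must take over the confirmatory decision, because that is a trade-off on which statisticians differ.

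**What to change.** 1. **Protocol 6.3.1:** restate power and the effective one-sided level for the analysis actually specified (jump to reference, Rubin pooling), with a range over missingness such as 10–35%. Say that the present 80% is for fully observed data.
2. **SAP 5.6.1:** keep Rubin's interval and p-value for the confirmatory decision and state that they are conservative by choice.
3. **SAP 5.6.1:** pre-specify, as supplementary, a bootstrap interval for the same point estimate. It resamples subjects within arm and repeats the imputation and ANCOVA each time.

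This costs some wording and a short program, with no new data and no change to estimand or point estimate. The stated power becomes less favourable. The supplementary interval takes the jump-to-reference assumption as exact, narrows as missingness rises, and is close to an observed-case test; the SAP should say so. Keeping Rubin for the decision also avoids moving the only confirmatory test to a smaller standard error in an open-label trial whose SAP (change log, section 7.0) has already been revised after the first patient's first visit.

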5.5.2 Patient Reported Outcomes

Missing endpoint data will be imputed for each of the WLQ-8 and WPAI:SHP summary scores at month 12 (visit 13). These data will be used for the analysis of the primary estimand for the secondary PRO endpoints.

The primary approach for imputation of the missing PRO summary scores at visit 13 will be similar to that described for body weight (Section 5.5.1). The imputation model is a linear regression of the PRO summary score at visit 13 with gender (male/female), BMI (kg/m²) in categories 30-<35, 35-<40, ≥40 as factors and baseline PRO summary score as covariate. The imputation approach will be repeated separately for each of the five WLQ-8 summary scores and four WPAI:SHP summary scores, as warranted.

